### **14 DATA MANAGEMENT**

Study data will be collected using paper and/or electronic case report forms (CRFs). Data will be entered into a study specific database in one of two ways or a combination of the following:

- Center research personnel will enter study data directly into an electronic case report form which functions as an electronic data capture screen for the study database.
- Center research personnel will enter study data onto paper CRFs, which will be submitted to the Sponsor or assigned designee.

The Sponsor or designee will follow standardized procedures for data review, database cleaning and issuing/resolving queries. Procedures for data verification, validation, security and data retention will be followed in order that the study data reported are complete, accurate and consistent with source data.

For the purpose of data analysis and presentation, the data of the original data set may be manipulated and additional variables calculated when necessary. Once the study data are completely entered, reviewed and checked, the study database will be locked and no further changes will be made.

### **15 POLICY FOR PUBLICATION AND PRESENTATION OF DATA**

The results of the study will be published by the PILLAR III Study Group (PSG). In addition to overall principal investigator, additional authors listed separately on the manuscript will be selected based on scientific input on the design of the study, interpretation of results, participation in manuscript preparation and on enrollment numbers. The final number of authors will depend on the journal's publication guidelines. All participating centers will be acknowledged in the main study manuscript.

The Sponsor also encourages the scientific publication of data from clinical research studies. However, Investigators may not present or publish partial or complete study results individually without participation of the study Principal Investigator as well as the Sponsor. The Principal Investigators and the Sponsor may propose appropriate scientific manuscripts or abstracts from the study data. All proposed publications must be reviewed and commented on by the Sponsor before submission for publication. The detailed procedures for the review of publications are set out in the clinical trial agreement entered into with the Sponsor in connection with this study. These procedures are in place to ensure coordination of study data publication and adequate review of data for publication against the validated study database for accuracy. Names of all

Investigators and Sponsor representatives responsible for designing the study and analyzing the results will be included in the publication(s).

6.2 Analysis of secondary efficacy endpoints.....	17
7. Evaluation of Safety.....	18
7.1 Adverse events.....	19

	Forms			
	Title	Statistical Analysis Plan Template		
	Code	Version	Effective Date	Page
	FRM_ST03_032	01	23 Apr 2015	4 of 20

7.2	Adverse Device Effect (ADE)	19
7.3	Serious Adverse Event (SAE).....	19
7.4	Unanticipated Adverse Device Effect (UADE).....	19

	Forms			
	Title	Statistical Analysis Plan Template		
	Code	Version	Effective Date	Page
	FRM_ST03_032	01	23 Apr 2015	5 of 20

Abbreviations

ADE	Adverse device effect
AE	Adverse event
AR	Anterior Resection
ASA	American Society of Anesthesiologists
AT	As-Treated
BMI	Body Mass Index
CFR	Code of Federal Regulations
CRF	Case Report Form
CT	Computerized Tomography
DSMC	Data and Safety Monitoring Committee
DRSI	Disposable Rigid Scope Introducer
FDA	Food and Drug Administration
GCP	Good Clinical Practice
GI	Gastrointestinal
HD	High Definition
IA	Imaging Agent
IBD	Inflammatory Bowel Disease
ICH	International Conference on Harmonization
ICG	Indocyanine Green
IMA	Inferior Mesenteric Artery
IMV	Inferior Mesenteric Vein
IPAA	Ileal Pouch – Anal Anastomosis
IR	Independent Radiologist
IRB	Institutional Review Board
IV	Intravenous
LAR	Low Anterior Resection
MELD	Model for End-Stage Liver Disease
mITT	Modified Intent-to-Treat
NGT	Nasogastric Tube
NIR	Near-Infrared
NPO	Nil per Os
PFN	Perfusion
PILLAR II	Perfusion Assessment in Laparoscopic Left Anterior Resection Multicenter study
PINPOINT	PINPOINT Endoscopic Fluorescence Imaging System
PO	Per Os

	Forms			
	Title	Statistical Analysis Plan Template		
	Code	Version	Effective Date	Page
	FRM_ST03_032	01	23 Apr 2015	6 of 20

POD	Post-operative Day
PP	Per-Protocol
PSG	PILLAR III Study Group
SAE	Serious Adverse Event
SAP	Statistical Analysis Plan
STD	Standard
US	United States
UADE	Unanticipated Adverse Device Effect
VIS	Visible

Revision History

Document Version	Changes Made	Document Date
0.1	Original based on Protocol version 1.4	07 Nov 2016
1.0	Final	10 Apr 2017

	Forms			
	Title	Statistical Analysis Plan Template		
	Code	Version	Effective Date	Page
	FRM_ST03_032	01	23 Apr 2015	7 of 20

1. Introduction

This study will investigate the effectiveness of assessing perfusion of colon and rectal tissue using PINPOINT endoscopic fluorescence imaging (PINPOINT) or SPY Elite intraoperative imaging in reducing the post-operative anastomotic leak rate in low anterior resection (LAR).

2. Study Objectives

Primary objective is to demonstrate an improvement in post-operative anastomotic leak rate in low anterior resection procedures where colon and rectal tissue perfusion is evaluated using PINPOINT® endoscopic fluorescence imaging or SPY Elite® Intraoperative Imaging as an adjunct to standard surgical practice compared to surgical procedures performed according to standard surgical practice alone.

Secondary objectives are the following:

- To evaluate the ability of the PINPOINT system or SPY Elite system to provide sufficient visualization for assessment of blood flow and related tissue perfusion during the procedure.
- To evaluate the effectiveness of assessing perfusion of colon and rectal tissue using PINPOINT or SPY Elite in reducing the rate of post-operative abscess requiring surgical management.

3. Study Design

3.1 General design and plan

This is a randomized, controlled, parallel, multicenter study to determine the reduction in post-operative anastomotic leak rate in low anterior resection (LAR) procedures where colon and rectal tissue perfusion is evaluated using PINPOINT or SPY Elite as an adjunct to standard surgical practice compared to surgical procedures performed according to standard surgical practice alone. Subjects will be enrolled at up to 40 centers in North America through March 31, 2017. The study sample size will depend on the number of subjects enrolled.

3.2 Visit Schedule and Visit Windows

Baseline/Screening Procedures (Day -30 to Day 0)

After signing the informed consent form, subjects will be assigned a screening and be evaluated for eligibility into the study.

The following procedures will be conducted during the baseline assessment:

	Forms			
	Title	Statistical Analysis Plan Template		
	Code	Version	Effective Date	Page
	FRM_ST03_032	01	23 Apr 2015	8 of 20

- Collection of demographics, surgical risk factors, pre-operative diagnosis.
- Vital signs (heart rate and blood pressure), height and weight.
- Serum tests (bilirubin, sodium, creatinine and INR) for MELD Score.
- Pregnancy test (urine test or institution standard of care) for females of childbearing potential.

Day 0 Procedures

On Day 0, the following will be completed before randomization and surgery:

- Serum hemoglobin, prealbumin, and albumin measurement.

During anesthesia, subjects will be randomized. Subjects are considered enrolled upon randomization.

According to the randomization assignment, subjects in the PERFUSION arm will receive perfusion assessment with PINPOINT and/or SPY Elite during surgery and undergo surgery according to the surgeon's standard practice. Subjects randomized to the Standard arm will undergo the surgery according to the surgeon's standard practice only. All subjects will receive the hospital/institution and surgeon's standard pre-operative and post-operative care with the addition of any study specific requirements.

An intra-operative measurement of hemoglobin should be performed at the time of anastomosis if the subject experiences a hypotensive event requiring intraoperative management (e.g. use of vasopressors) or blood loss greater than 500 ml at the time of anastomosis.

Post-operative Follow-up Visits (Day 1 to Last Study Visit)

Subjects will have standard of care assessments throughout the study according to the hospital/institutions standard procedures as well as study specific visits on postoperative Day 1, the date of discharge, Week 8 (56 ±14 days) and the date of ileostomy closure, if applicable. Subjects will be assessed for the following throughout the study:

- Serum hemoglobin measurement (Day 1).
- Evidence of anastomotic leak.
- Assessment and grading of post-operative complications.
- Concomitant medications and procedures.
- Adverse events/adverse device effects.

Subjects with a discharge date later than Week 8, who did not have an ileostomy, will have the last study visit on Week 8 ±14 days.

Diverted patients should receive routine endoscopic and/or contrast enema evaluation of the anastomotic region, between 3 weeks post-surgery and the Week 8 visit.

	Forms			
	Title	Statistical Analysis Plan Template		
	Code	Version	Effective Date	Page
	FRM_ST03_032	01	23 Apr 2015	9 of 20

Subjects who present with a clinical suspicion of anastomotic leak during the study will have a CT scan with PO and, if necessary (e.g., presence of a diverting ileostomy), rectal contrast to confirm.

Table 1 below presents the schedule of events for this study.

	Forms			
	Title	Statistical Analysis Plan Template		
	Code	Version	Effective Date	Page
	FRM_ST03_032	01	23 Apr 2015	10 of 20

Table 1: Schedule of Assessments

Procedure	Baseline (Day -30 to Day 0)	Day 0 (Operative Phase)			Post-Operative Follow-Up		Ileostomy Endoscopy/ Contrast Enema (Week 3 to Week 8 ±14d)	Week 8 (56±14d)
		Pre-Op	Intra-Op	Post-Op	Day 1 (24±12 hrs.)	Date of Discharge ^a		
Informed consent	X							
Demography	X							
Vital signs, height, weight	X							
Surgical risk factors	X							
Pre-operative diagnosis	X							
Pregnancy test (record in source only)	X							
Inclusion/exclusion criteria	X							
Serum sodium, bilirubin, creatinine and INR for MELD Score	X							
Hemoglobin, Albumin, Pre-albumin		X	X ^c		X			
Randomization (in OR, during anesthesia)			X					
LAR surgical procedure			X					
Imaging agent administration (treatment group only)			X					
Perfusion Assessment (Perfusion arm only)								
Proximal transection margin			X					
Mucosal aspect of completed anastomosis								
Document actual surgical technique				X				
Anastomotic leak assessment				X	X	X		X
Surgical Complication assessment/grading			X	X	X	X		X
Endoscopy and/or contrast enema - Ileostomy subjects (between 3 & 8 wks.)							X ^b	
Concomitant medications and procedures	X	X	X	X	X	X		X
Adverse events/adverse device effects		X	X	X	X	X		X ^d

	Forms			
	Title	Statistical Analysis Plan Template		
	Code	Version	Effective Date	Page
	FRM_ST03_032	01	23 Apr 2015	11 of 20

- a Subjects with a discharge date later than Week 8, who did not have an ileostomy, will be followed until Week 8 ±14d.
- b All subjects with a diverting ileostomy must have endoscopy and/or contrast enema between 3 weeks post-surgery and the Week 8 visit.
- c Hemoglobin measurement at time of anastomosis if subject had any hypotensive events or blood loss over 500 ml at time of anastomosis
- d All subjects with adverse events thought to be related to the LAR will be followed until resolution or deemed chronic.

	Forms			
	Title	Statistical Analysis Plan Template		
	Code	Version	Effective Date	Page
	FRM_ST03_032	01	23 Apr 2015	12 of 20

3.3 Sample size justification

The sample size for this study will include all subjects enrolled through March 31, 2017. No formal sample size calculations were carried out for this study.

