**Sample Size and Statistical Analysis:**

The PILLAR III study is designed to allow a single mid-trial reassessment of sample size, employing the method of Mehta and Pocock. A minimum of 450 and a maximum of 1000 subjects will be enrolled at up to 30 centers. The trial will utilize a group sequential design with Pocock stopping boundaries with a planned sample size of 800 subjects. A futility boundary will also be incorporated. A single interim analysis will be conducted on the first 450 subjects enrolled with assessment of the primary endpoint. If the stopping boundary for trial success is not met at this interim analysis point and futility is not declared, the Mehta and Pocock method of sample size re-estimation based on promising zones will be applied to evaluate whether an increase in sample size above the planned 800 subjects is warranted (up to a maximum of 1.25 times the original planned sample size, i.e. 1000 subjects).

At the time of the interim analysis, the primary objective null hypothesis will be tested against the one-sided alternative hypothesis that the anastomotic leak rate in the PERFUSION arm is less than that experienced with the STANDARD surgical approach. If the p-value is less than a pre-specified threshold based on the Pocock stopping boundary, the null hypothesis will be rejected, whereas if the p-value is greater than the futility threshold, the trial will be considered futile. In either of these eventualities, no new enrollments will occur, and follow-up will only continue per regulatory requirements. However, if the p-value falls between these two thresholds, an evaluation of conditional power will be made to determine if a re-estimated larger sample size is warranted. The trial will then continue to either the planned sample size of 800 subjects or the re-estimated sample size of up to a maximum of 1000 subjects.

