## **4 SELECTION AND WITHDRAWAL OF SUBJECTS**

### **4.1 Number of Subjects**

A minimum of 450 and a maximum of 1000 subjects will be enrolled.

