### 10.4 Adaptive Design and Sample Size Considerations

Available literature does not provide a precise estimate of the expected anastomotic leak rate in the control group or in the treatment group. As previously described, anastomotic leak is reported to occur in a wide range of 3-20% of the time in colorectal surgery and the risk increases for lower anastomoses. In the limited prior experience with the PINPOINT PILLAR II study (n=139 subjects) the anastomotic leak rate was 1.4%.

Given the limited knowledge of control incidence and the treatment effect size, the PILLAR III study will employ an adaptive design with a mid-trial sample size re-assessment. The planned sample size is  $N = 800$ , with possible early stopping for efficacy or futility at an interim analysis at  $N = 450$ . The planned total of 800 subjects will provide >80% power to test the one-sided hypothesis of superiority for treatment over control in leak rate at the 0.025 significance level if the true leak rates  $p_c$  and  $p_t$  are 12.5% and 6.25% (a 50% relative reduction), assuming a two-look group sequential analysis plan (with Pocock alpha-spending bounds and analyses at 450 and 800). If the trial does not stop at  $N = 450$ , sample size will be assessed at that time and possibly increased up to a maximum of 1000 subjects, using the method of Chen et al. and described in Mehta and Pocock.

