For the primary objective, the following analysis plan will be used After  $N = 450$  subjects have been enrolled, randomized and treated and the primary outcomes observed. The primary objective null hypothesis will be tested against the one-sided alternative hypothesis above. If  $p < 0.0169$  (as determined by the Pocock alpha spending function), the null hypothesis will be rejected, whereas if  $p \geq 0.4$ , the trial will be considered futile. However, if  $0.0169 \leq p < 0.4$  an assessment of whether to increase the sample size above the planned 800 subjects will be made in accordance with the “promising zone” method of Mehta and Pocock. If the conditional power (CP) at  $N = 800$  subjects based on the available data at the time of the interim analysis is less than 0.5 or at least 0.8, enrollment will continue to 800 subjects and the final analysis will be conducted. Alternatively, if  $0.5 \leq CP < 0.8$ , the sample size will be re-estimated in accordance with the Mehta and Pocock method for sample size re-estimation up to a maximum of 1000 subjects. (The recalculated sample size cannot be less than 800 subjects based on the interim analysis.) The final sample size is calculated by determining the added sample size needed to achieve the target conditional power of 80% given the data at the time of the interim analysis, subject to a maximum of 1000 subjects. This method guarantees control of the type I error while still allowing standard inferential methods of analysis.

**10.5 The planned sample size 800 . is based on the following rationale: If the true leak rates  $p_c$  and  $p_t$  are 12.5% and 6.25% (a 50% relative reduction), respectively, then PASS 13 indicates that , a two-look group sequential analysis plan (with Pocock alpha-spending bounds and analyses at 450 and 800) achieves 81.6% power to reject the null hypothesis at a one-sided significance level of 0.025. Study Populations for Analysis**

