6.1 Analysis of primary endpoint

The primary objective is to demonstrate an improvement in post-operative anastomotic leak rate in low anterior resection procedures where colon and rectal tissue perfusion is evaluated using PINPOINT or SPY Elite near infrared fluorescence imaging as an adjunct to standard surgical practice compared to surgical procedures performed according to standard surgical practice alone.

$$H_0: p_t = p_c$$

$$H_1: p_t < p_c$$

Where p_t and p_c represent the expected population incidences of post-operative anastomotic leaks in the treatment (PERFUSION) and control groups, respectively. Within their respective treatment groups, p_t and p_c will be estimated as the number of subjects who experience a post-operative anastomotic leak divided by the number of subjects who either are included in the numerator or are known to be free of such leaks as of the 8 weeks visit. Subjects without a known anastomotic leak but with less than 6 weeks of follow-up (i.e., insufficient follow-up to declare them "leak-free") will not be included in these estimates.

Analysis of these hypotheses will be conducted using a z-test (i.e., normal approximation to the binomial distribution, using a pooled variance estimate and without continuity correction), using a (one-sided) significance level of 0.025.

A secondary analysis of the primary endpoint will be carried out on the As-treated population as well as on the PP population.

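### SAP 3.3 denies the sample size calculation that Protocol 10.4 contains, and drops the two-look design without saying whether the 450-subject look was taken

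*SAP*

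**What the plan says.** **Protocol.** Section 4.1 sets limits: "A minimum of 450 and a maximum of 1000 subjects will be enrolled". Section 10.4 plans 800 subjects, "with possible early stopping for efficacy or futility at an interim analysis at" 450. At that look, for p < 0.0169, "as determined by the Pocock alpha spending function), the null hypothesis will be rejected"; at p ≥ 0.4 the trial is futile; in between, the final size may be raised to at most 1000. For true leak rates of 12.5% and 6.25%, the paragraph that runs into the 10.5 heading says that the two-look plan "achieves 81.6% power to reject the null hypothesis at a one-sided significance level of 0.025". The Protocol Summary says what follows if neither boundary is met: "The trial will then continue to either the planned sample size of 800 subjects or the re-estimated sample size", up to 1000. Section 10.7 gives the primary test an overall type I error of 2.5%, and says that the secondary objectives are tested once, at the interim or at the final analysis.

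**SAP.** Section 3.1: "Subjects will be enrolled at up to 40 centers in North America through March 31, 2017". Section 3.3 makes that date the sample size rule and adds "No formal sample size calculations were carried out for this study". Section 6.1 specifies one pooled z-test "without continuity correction), using a (one-sided) significance level of 0.025". Section 6.2 repeats the gatekeeping of Protocol 10.7 but leaves out its sentence on interim or final testing. The supplied SAP text has no interim analysis, spending function, futility rule, re-estimation, or N of 450, 800 or 1000.

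**The concern.** Set against the supplied protocol, the sentence in SAP 3.3 is untrue. The larger matter is what goes with it. Under the protocol, 0.025 is the total level of a two-look design; in the SAP, the same 0.025 is given to one test. Both uses are sound on their own terms. Which one applies depends on a fact that the SAP omits: whether outcomes were tested by arm at 450 subjects.

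Two things are at stake. First, 81.6% power belongs to a design that runs to 800 unless it stops at the look. It does not describe a trial closed by date, and the SAP offers no figure in its place. Second, the study is labelled pivotal, and its primary test is the gate to secondary objectives meant to support labelling. A reader must be able to confirm that the primary test keeps its 2.5%.

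**Working it through.** **Inputs.** From Protocol 10.4 and the paragraph attached to the 10.5 heading: control rate 0.125, PERFUSION rate 0.0625, looks at 450 and 800, Pocock spending, total one-sided 0.025. From Protocol 10.3: pooled z-test, no continuity correction. From Protocol 5.1: 1:1 allocation. Neither document gives the number enrolled, so every final N below other than the planned 800 is an assumption.

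**1. The protocol's own figures.**

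- Spent at the look: 0.025 × ln(1 + (e − 1) × 450/800) = 0.025 × ln(1.9665) = 0.0169, so z1 = 2.122. This matches the protocol.
- Left for the final look: 0.0250 − 0.0169 = 0.0081. Solving P(Z1 < 2.122, Z2 > z2) = 0.0081 with correlation √(450/800) = 0.75 gives z2 = 2.220, a final level of 0.0132. The protocol prints no final level; this one is derived.
- Mean rate 0.09375; pooled variance term 2 × 0.09375 × 0.90625 = 0.16992. Expected z: 0.0625 × √(225/0.16992) = 2.274 at 450, and 0.0625 × √(400/0.16992) = 3.032 at 800.
- Power = 0.560 at the look + 0.256 at the end = 0.816. The stated 81.6% is correct.

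**2. If no look was taken.** One test at 0.025 has type I error 2.5%. Its power for 12.5% versus 6.25% is

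Φ[(0.0625 × √(N/2) − 1.960 × √0.16992) / √0.16797],

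where 0.16797 = 0.125 × 0.875 + 0.0625 × 0.9375. At N = 450: (0.9375 − 0.8079)/0.4098 = 0.316, so power is 62%.

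| Assumed evaluable N | Power, single test at 0.025 |
|---|---|
| 300 | 46% |
| 400 | 57% |
| 450 | 62% |
| 600 | 75% |
| 800 | 86% |

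**3. If the look was taken at 0.0169 and the trial continued.** Testing again at 0.025 (z = 1.960) gives type I error 0.0169 + P(Z1 < 2.122, Z2 > 1.960), with correlation √(450/N). The level that holds 2.5% keeps the 0.0169 and solves for the remaining 0.0081 at the same correlation.

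| Assumed final N | Correlation | Type I error with final 0.025 | Final level that holds 2.5% |
|---|---|---|---|
| 500 | 0.949 | 0.02805 (2.8%) | 0.0210 |
| 600 | 0.866 | 0.03140 (3.1%) | 0.0166 |
| 800 | 0.750 | 0.03446 (3.4%) | 0.0132 |

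These ignore the futility rule. If it is always obeyed, the figure at 800 is 3.41%.

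The calculation must keep the 0.0169. Re-evaluating the spending function at 450/600 would spend 0.0207 at the look and give a final level of 0.0120, which does not describe a look tested at 0.0169.

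**4. Cost of the stricter level.** At N = 600, two-look power with 0.0169 then 0.0166 is 72.0%, against 74.9% for a single test at 0.025.

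**The case against.** The strongest reply is that the SAP is simply a fixed, single-analysis plan. It has no interim section and tests once at one-sided 0.025. If enrolment ended before 450 subjects had outcomes, the planned look could not have happened. On that reading the test is valid and the fault is one loose sentence. This stands as far as validity goes. It does not rescue the sentence, and it does not replace the 81.6%.

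A reader might infer three stronger things, none of which the documents support.

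- *That type I error is inflated.* This needs a look to have been taken and the trial to have continued. Neither document says so.
- *That the closing date was chosen after seeing results by arm.* Nothing points to this. The Protocol Summary and Protocol section 11 plan a start in the first half of 2015 and about 24 months of enrolment, so 31 March 2017 lies close to the planned end. That makes the date unremarkable, though it does not explain dropping the 800.
- *That the two documents use different significance levels.* Both state one-sided 0.025. The conflict is on sample size and interim design.

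There is also a version limit. The SAP revision history cites protocol version 1.4, and the version of the supplied protocol is not visible. If they differ, part of the contradiction may come from an intervening change. The SAP would still need to say which design applies.

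Finally, the 95% confidence intervals planned in SAP 4.1 will show the precision achieved. That is true, and power at the enrolled N adds only modestly to them. It is asked for because SAP 3.3 is headed as a justification and contains none.

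**Conclusion.** SAP 3.3 is wrong as written against the supplied protocol and should be corrected. The protocol's calculation exists and is arithmetically right. The SAP abandons the design behind it without saying so, and 81.6% no longer describes the trial. The documents do not settle which design governs the primary test.

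The established fault is this inconsistency and the missing statement about the look, not an error in the test itself. With no look, 0.025 is valid and power runs from 46% to 86% across assumed evaluable sizes of 300 to 800, at the protocol's leak rates. The excess in type I error (0.3 to 0.9 percentage points across assumed final sizes of 500 to 800) arises only if the look was taken at 0.0169, the trial continued, and 0.025 was used again.

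**What to change.** **SAP 3.3.** Delete the sentence denying a calculation. Cite the Protocol 10.4 calculation, say that enrolment closed by date, and say that the 800 target and its 81.6% power no longer apply. Give the number enrolled and the power of the single test at that number. The evaluable number comes later, since SAP 6.1 requires six weeks of follow-up for a subject without a leak.

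**SAP 6.1.** State whether the 450-subject look was taken, checked against the records of the data and safety monitoring committee, which Protocol 13.3 makes responsible for reviewing the interim analysis. State that the cut-off was set without outcome data by arm, if that is so.

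- *No look taken:* declare a fixed-sample test at one-sided 0.025 and record the departure from Protocol 10.4.
- *Look taken:* keep the 0.0169 already spent and spend only the rest of 0.025 at the actual final information. The final level is 0.0210 at 500, 0.0166 at 600 or 0.0132 at 800.

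**Cost.** Wording only in the first case. In the second, slightly lower power: about 72% instead of 75% at 600. Neither case needs more patients.
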